In study INCB 18424-132, multiple oral doses of 25 mg BID and 50 mg daily and BID have been administered with monitoring of adverse events, clinical laboratories, PK and pharmacodynamic parameters. The preliminary unaudited pharmacodynamic draft data available indicate that multiple doses of INCB018424 are able to inhibit interleukin-6 induced STAT3 phosphorylation in a dose dependent manner, similar to data obtained in the single dose studies. The data on day 1 and day 10 demonstrated similar levels of inhibition of STAT3 phosphorylation, indicating a lack of cumulative biological activity. From an evaluation of the safety data obtained in this study, the preliminary conclusion is that the INCB018424 50 mg BID dose is considered too high for healthy volunteers and patients without serious diseases. Dosing in these populations should be limited to 25 mg BID or lower and up to 50 mg daily, although higher doses than 50 daily may be safe but have not been tested beyond single doses. However, in patients with malignancies dose escalation could continue until the maximum tolerated dose is achieved due to the different benefit-risk ratio in these subjects and because these patients may respond differently.

Under IND No. 77,456, INCB018424 has also been dosed to three patients with multiple metaplasia with myelofibrosis at 25 mg BID for over five months with clinical benefit but without notable toxicity. In this study four patients have also been dosed at 50 mg INCB018424 BID but, according to protocol, dosing was halted after two of four subjects presented with significant reductions in peripheral blood neutrophils and platelets. Subsequently, according to protocol, three additional patients have been treated at the 25 mg BID dose for at least 1 month to establish this dose as the MTD in this population.

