4. TREATMENT PLAN

4.1 Dose of INCB018424 and Treatment Cycle

This is a phase II study of oral INCB018424 in patients with relapsed/refractory AML, ALL, and MDS (including CMML), and blast phase or tyrosine kinase refractory CML. The starting dose of INCB018424 will be 25 mg po twice daily, which has been determined to be the maximum tolerated dose in patients with myelofibrosis with myeloid metaplasia and a dose that is tolerated for ten days in normal human volunteers.

INCB018424 will be administered orally at a dose of 25 mg BID for 7 days each week for 4 weeks (cycle number 1). Patients will be evaluated after 1 full cycle of therapy (28 days) for response. Responding patients or patients with stable disease will be allowed to continue on study at a dose of 25 mg INCB018424 BID until progression. The response assessment for the purpose of study statistical evaluation will be after two cycles (8 weeks) of therapy. Patients with progressive disease, based on clinical and laboratory evaluation, will, at the discretion of the Investigator, either be removed from the study or, as long as the 25 mg BID dose has been well tolerated, dose escalated to 50 mg INCB018424 BID. In instances of dose escalation to 50mg BID, patients will be evaluated after

1 full cycle of therapy (28 days) for response and toxicity. At that point, patients with continued progressive disease, based on clinical and laboratory evaluation, will be removed from the study. In instances of dose escalation, the response assessment for the purpose of study statistical evaluation will be after two cycles (8 weeks) of therapy at the 50 mg BID dose.

Patients with chronic phase CML who have failed at least 2 prior tyrosine kinase inhibitors and do not have a standard transplant option will be assessed for response after 3 months of therapy in the absence of loss of disease control and they may continue therapy if they demonstrate any clinical benefit. Patients with chronic phase CML will not be allowed to have the dose escalation as this population has less of a life-threatening disease situation.

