Patients who, in the opinion of the Investigator, are demonstrating cytopenias not thought to be related to disease progression and who may be receiving benefit from treatment may, at the discretion of the Investigator, be dose adjusted to a lower dose of INCB018424 BID or an equivalent dose given daily (see section on dose modifications below). Studies in subjects with myelofibrosis with myeloid metaplasia using different doses and schedules of INCB18424 may be used as a guide to dose adjustments in this study.

Patients will initiate the first cycle of therapy at MDACC. They will have weekly visits at their local physician's office with physical exam and review of symptoms during cycle one. In the absence of intolerable side effects, patients may return to the local oncologist for laboratory tests, but only MDACC investigators can make treatment decisions. Patients will return to MDACC every 4 weeks to be evaluated and receive their new supply of study medication. For the second and third cycle, patients will return to MDACC every 4 weeks to be evaluated and receive their new supply of study medication. Subsequently, patients will return to MDACC every three months. Because of drug stability issues, some patients may have to continue to be seen on a monthly basis to have the drug provided.

For toxicity evaluation, patients enrolled in the study will be considered in 2 cohorts (I) those with relapsed/refractory AML, ALL, and MDS (including CMML), and blast phase CML, and (II) those with chronic phase CML. At any time after 6 patients are enrolled in cohort I (including AML, ALL, MDS, blast phase CML patients), if 30% or more patients experience grade 3 or 4 toxicity thought to be directly related to INCB018424 and lasting longer than 2 weeks, then we will stop that cohort of the trial. At any time after 6 patients are enrolled in cohort II (including chronic phase CML patients), if 15% or more patients experience grade 3 or 4 toxicity thought to be directly related to INCB018424 and lasting longer than 2 weeks, then we will stop that cohort of the trial.

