4.2 Administration of INCB018424

This is an open label, non-randomized, study of INCB018424, administered orally to patients with relapsed/refractory AML, ALL, and MDS (including CMML), and blast phase or tyrosine kinase refractory CML. The study of INCB018424 in each disease listed will be conducted in two parts. The first part is intended to enroll a maximum of 10 patients within each of the four disease categories included in this study and to identify whether significant benefit is observed. If a minimum of one patient shows benefit that is considered significant, there will be an expanded cohort of 20 additional patients treated in that arm of the study.

Patients will receive 50 mg/day administered orally in two divided doses (i.e., BID: every 12 hours \pm 2 hours). Within each arm of the study, three patients will be initially treated and observed for toxicity for one treatment cycle (28 days) before the additional seven patients are entered. Dose reduction will be considered if the number of patients experiencing grade 3 or higher toxicities exceed 2/3, 3/4, 4/7, 5/10, 6/14, 7/18, 8/22, 9/26. Treatment will be administered primarily on an outpatient basis, but can be administered as an inpatient if the patient is hospitalized for other reasons.

The 5 mg tablets have been shown to be stable when stored up to one month at 25° C/60%RH and 40° C/75%RH; the 25 mg tablets have been shown to be stable when stored for three months at 25° /60%RH and 40° /75%RH. (25° C = 77° F, 40° C = 104° F).

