Hold until recover to NCI CTC AE grade 0-2 If recovery occurs within 2 weeks after treatment has been held, dose should be reduced to 10 mg or 15 mg BID. At the discretion of the investigator and if the patient is considered to be benefiting, the patient will receive an intermittent dose schedule, alternating treatment periods and recovery periods at the 25 mg BID dose. i.e alterations to the dose and schedule that is thought to be beneficial to the patient in the responding patients may be allowed after discussion with IRB, FDA and the PI.

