- i. Bone marrow aspiration or biopsy will be taken during the screening phase (within 4 weeks of starting drug), and at start of Cycle 4 (± 7 days), Cycle 7 (± 7 days), and thereafter at start of each 6th subsequent cycle (+/- 7days). Evaluation will include staining for fibrosis and cytogenetics if abnormal prior to therapy. Cytogenetic studies will be repeated only in patients with abnormalities at baseline, on Day 1 of Cycles 4 and 7 and thereafter on Day 1 of each 6th subsequent cycle(+/-7days). If unable to obtain BM aspirate, cytogenetics may also be done on peripheral blood collected for PD/PK analysis.
- j. Instruct patient that the dose is to be taken at 12 hour intervals at approximately the same time each day. The first dose of each day should be taken in the morning.
- k. For Cycle 1, PK samples to be collected on Day 1 at pre-dose, 0.5, 1, 1.5, 2, 4, 6, and if possible 8 hours after administration of the morning dose of INCB018424. For Cycles 2 and 3, a PK sample will be collected at pre-dose on Day 1.
- I. For Cycle 1, plasma and whole blood PD samples will be collected on Day 1 at pre-dose and 2, hours after administration of the morning dose of INCB018424. For Cycles 2, 3, and each subsequent scheduled visit to MDACC, plasma and whole blood PD samples will be collected at pre-dose on Day 1. Final PD sample will be collected at End-Of–Study visit. Not all samples may be collected on all patients. See Appendix F.
- m. Adverse events (AEs) considered related to study medication must be followed until resolution, start of a different treatment therapy or no longer considered to be clinically relevant in the opinion of the investigator. During the treatment phase, AE assessment is required weekly at the local physician's office during 1st cycle of therapy. During the 2nd and 3rd cycles assessments are required every 4 weeks, and then every visit thereafter.
- n. Compliance should be checked at each scheduled clinical visit. Any unused drug in sealed bottles will be returned to Incyte or its designee. MDACC will follow internal procedures to destroy and dispose of unused drug in open/unsealed bottles.

Protocol Number 2007-0925 October 13, 2008 Page 17 of 36

o. End-of-Study procedures are to be completed if patient completes study or at anytime patient terminates treatment early in the study.

5.2.1 Cycle 1

5.2.1.1 Cycle 1 - Day 1

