9.1.1 Selection of Sample Size

This phase II study will use a Gehen's design. Assuming a null response rate of 0%, targeting a 15% response rate and power=80%, the trial will initially enroll 10 patients in each disease category: 1) AML; 2) ALL; 3) MDS; and 4) CML. If at least one response is achieved in the 10 patients in a disease

Category, then a total of 30 patients will be enrolled in this disease category. Thirty patients will provide a confidence interval for response rate with half-width=0.13, assuming the true response rate is 15%. The total sample size is 120.

For toxicity evaluation, patients enrolled in the study will be considered in 2 cohorts (I) those with relapsed/refractory AML, ALL, and MDS (including CMML), and blast phase CML, and (II) those with chronic phase CML. At any time after 6 patients are enrolled in cohort I (including AML, ALL, MDS, blast phase CML patients), if 30% or more patients experience grade 3 or 4 toxicity thought to be directly related to INCB018424 and lasting longer than 2 weeks, then we will stop that cohort of the trial. At any time after 6 patients are enrolled in cohort II (including chronic phase CML patients), if 15% or more patients experience grade 3 or 4 toxicity thought to be directly related to INCB018424 and lasting longer than 2 weeks, then we will stop that cohort of the trial.

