9.3.1 Adverse Events

Severity of adverse events will be based on the NCI–CTCAE v3.0 (NCI Common Terminology Criteria for Adverse Events, Publ. Aug 9, 2006). The subset of adverse events that are considered by the Investigator to have a possible or probable relationship to study medication will be considered to be treatment-related adverse events. If the Investigator does not specify the relationship of the adverse event to study medication, the adverse event will be considered to be treatment-related. The incidence of adverse events and treatment-related adverse events will be tabulated.

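### The cohort I 30% toxicity stop pools events at 25 mg BID and 50 mg BID, and no aggregate check is specific to the escalated dose

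*Combined protocol and SAP*

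**What the plan says.** Section 4.1 states that for toxicity "patients enrolled in the study will be considered in 2 cohorts": cohort I (AML, ALL, MDS including CMML, and blast phase CML) and cohort II (chronic phase CML). After 6 patients are enrolled, cohort I stops "if 30% or more patients experience grade 3 or 4 toxicity thought to be directly related to INCB018424 and lasting longer than 2 weeks". Section 9.1.1 repeats the rule. Neither place mentions dose, and the only consequence given is stopping the cohort.

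Under section 4.1, a cohort I patient with progressive disease may, at the investigator's discretion, be, "as long as the 25 mg BID dose has been well tolerated, dose escalated to 50 mg INCB018424 BID". Response and toxicity are reviewed after 28 days at the higher dose. Chronic phase CML patients may not escalate. Section 4.1 calls 25 mg BID the maximum tolerated dose in myelofibrosis, and section 2.2.3 reports that at 50 mg BID in that disease "dosing was halted after two of four subjects presented with significant reductions in peripheral blood neutrophils and platelets".

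The other aggregate check is in section 4.2: "Dose reduction will be considered if the number of patients experiencing grade 3 or higher toxicities exceed 2/3", continuing to 9/26. It follows the statement of 25 mg BID dosing and is not split by dose. Section 4.5 manages individual patients (for grade 3-4 non-haematological toxicity, "Hold until recover to NCI CTC AE grade 0-2"). For reporting, section 9.3.1 says "The incidence of adverse events and treatment-related adverse events will be tabulated", with no split by dose.

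**The concern.** Safety and tolerability is a secondary objective. Cohort I patients may receive two doses, and the protocol itself gives reason to expect them to differ in toxicity. A pooled proportion can then mislead in two directions. An excess at 50 mg BID can be diluted by the patients who stay on 25 mg BID, so escalation continues past a level the protocol would not accept for the cohort as a whole. Conversely, 50 mg BID events can help close a cohort whose starting dose is tolerable.

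Section 4.1 does separate the doses for efficacy: escalated patients are assessed after two cycles at 50 mg BID. Safety monitoring has no counterpart.

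What is at stake is a decision during the trial. The data are not lost: adverse events are assessed on a schedule ("During the 2nd and 3rd cycles assessments are required every 4 weeks, and then every visit thereafter") and drug is dispensed at recorded visits, so dose at onset can be reconstructed.

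**Working it through.** **Plan's own figures.** Section 9.1.1 gives figures for efficacy only, and they reproduce: 1 − 0.85^10 = 0.803 (stated power 80%), and 1.96 × √(0.15 × 0.85/30) = 0.128 (stated half-width 0.13). No operating characteristics are given for the toxicity rule, so there is nothing to reproduce for it.

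**Inputs from the documents.** Threshold 30%; looks at any time after 6 patients; denominator all enrolled cohort I patients.

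**Assumed inputs, not in the documents.** 30 patients (AML, ALL and MDS at 10 each in the first stage); qualifying-event rate 10% at 25 mg BID and 50% at 50 mg BID; 3, 6 or 10 escalated; escalated patients have no qualifying event at 25 mg BID, because escalation requires that dose to be well tolerated. Ranges below cover looks starting at patient 6 or at patient 7.

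**Arithmetic of dilution.** Expected pooled proportion = (patients not escalated × 0.10 + patients escalated × 0.50)/30.

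- 10 escalated: (20 × 0.10 + 10 × 0.50)/30 = 7/30 = 23%.
- 6 escalated: (24 × 0.10 + 6 × 0.50)/30 = 5.4/30 = 18%.

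Both are below 30%. At 30 patients the rule needs 0.30 × 30 = 9 events. With 6 escalated, 5 of 6 (83%) at 50 mg BID plus 3 of 24 at 25 mg BID makes 8 of 30 (27%), which does not stop the cohort.

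**Simulation** (200,000 runs, random order, stop when events/n ≥ 0.30).

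| 50 mg BID events counted | Escalated | Pooled stop | No stop, final 50 mg BID proportion ≥ 30% |
|---|---|---|---|
| At enrolment | 10 | 0.56-0.62 | 0.33-0.39 |
| At enrolment | 6 | 0.33-0.41 | 0.50-0.58 |
| 8 enrolments later | 10 | 0.20-0.31 | 0.73-0.75 |
| 8 enrolments later | 6 | 0.13-0.18 | 0.74-0.77 |

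With 3 escalated, pooled stopping is 0.18-0.26 unlagged and 0.10-0.15 lagged. With no excess at 50 mg BID and events counted at enrolment, it is 0.08-0.14.

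**Why a lag.** Escalation follows a 28-day cycle and the event must last more than 14 days, so it cannot count before about day 28 + 14 = 42. The figure of 8 enrolments is an assumption about accrual.

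**End of monitoring.** With 10 escalated and the lag, pooled stopping is 0.20-0.22 if monitoring ends at the 30th enrolment, and 0.30-0.31 if events maturing afterwards also count. The lagged figures in the last column use the first convention. Under the second, a lower bound is P(final proportion ≥ 30%) − P(pooled stop):

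- 10 escalated: P(at least 3 of 10) = 968/1024 = 0.945, so at least 0.945 − 0.308 = 0.64 (or 0.945 − 0.296 = 0.65).
- 6 escalated: P(at least 2 of 6) = 57/64 = 0.891, so at least 0.891 − 0.175 = 0.72 (or 0.891 − 0.143 = 0.75).

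**Sensitivity.**

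- *50 mg BID rate of 30%, unlagged:* pooled stopping is 0.28-0.36 with 10 escalated and 0.18-0.27 with 6. The same bound gives a missed excess of at least 0.617 − 0.361 = 0.26 to 0.617 − 0.277 = 0.34 with 10 escalated, and at least 0.580 − 0.265 = 0.32 to 0.580 − 0.185 = 0.40 with 6.
- *90 patients, one third escalated, 50% rate, unlagged:* pooled stopping is 0.60-0.65 and missed excess 0.34-0.40.

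**The case against.** The strongest reply is that the plan treats 25 mg BID with optional escalation on progression as one strategy, and monitoring a strategy by disease cohort is defensible. Escalation is discretionary, needs good tolerance of 25 mg BID, is followed by a 28-day toxicity review, and is decided by investigators at one centre. Section 2.2.3 expressly contemplates escalation in malignancy. Holds and reductions may keep some events under 2 weeks. All of this stands. But these safeguards act on one patient at a time, and at the 28-day review only continued progression is named as a reason for removal. None shows a group excess at 50 mg BID.

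The 50% rate is also open to challenge. The 2 of 4 in section 2.2.3 were cytopenias in myelofibrosis with no grade or duration given, and section 8.1 treats myelosuppression as expected in leukaemia. The rate is an assumption, and a reader should not take 2 of 4 as an estimate of it. Dilution remains, at a smaller size, at 30%.

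A reader might infer that no aggregate check governs escalation at all. The documents do not support that. Stopping cohort I would end escalation too, and the section 4.2 boundaries also count patients across an arm. Neither is specific to 50 mg BID, however. The first section 4.2 look, at three patients over one cycle, is essentially at 25 mg BID; later looks may be mixed, and crossing a boundary only prompts consideration of a dose reduction.

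**Conclusion.** The concern holds. As written, the rule counts qualifying events regardless of dose, and a 50 mg BID proportion at or above the plan's own 30% limit can go unflagged while escalation continues. Under the assumed 10% and 50% rates with 6 to 10 of 30 escalated, this happens in 0.33 to 0.58 of trials without a lag and in about 0.73 to 0.77 with a lag of 8 enrolments (at least 0.64 to 0.75 if late-maturing events also count). The size depends on rates, escalated share and accrual that the documents do not give; the direction does not, so long as 50 mg BID is the more toxic dose.

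A reader might also infer that the pooled rule would usually close 25 mg BID wrongly, given stopping of 0.56 to 0.62 with 10 escalated. That figure counts 50 mg BID events at enrolment, which the escalation sequence rules out. With the lag, stopping is about 0.20 to 0.31 with 10 escalated and 0.10 to 0.18 with 3 to 6, against 0.08 to 0.14 with no excess (events at enrolment). Over-stopping is possible but secondary.

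Only cohort I is affected. The change should be made; confidence is medium because the magnitude rests on assumptions.

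**What to change.** 1. Derive dose at onset for every adverse event.
2. In section 9.3.1, tabulate related grade 3-4 events, and separately those lasting longer than 2 weeks, by dose at onset. Use patients treated at each dose as denominators, so escalated patients count in both.
3. In sections 4.1 and 9.1.1, keep the pooled stop. Add that, once 6 patients have escalated, further escalation is paused for review, not closed automatically, if 30% or more of escalated patients have a qualifying event at 50 mg BID.
4. Report any pooled stop with the dose at onset of its events.

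The cost is wording in three sections and one derived variable. The added check has limits. It does not operate below 6 escalations, and denominators are small: 3 of 10 has an exact 95% interval of 7% to 65%. It also pauses escalation at true rates below the limit. With 10 escalated, the chance of a pause is 7-14% at a true 50 mg BID rate of 10%, 18-27% at 15% and 32-42% at 20%, against 62-70% at 30% and 95-96% at 50%. With exactly 6 escalated it is 11%, 22%, 34%, 58% and 89% at the same five rates. These false pauses are tolerable because the consequence is a review.

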8. REGULATORY AND REPORTING REQUIREMENTS

Adverse event reporting will be as per the current NCI criteria and the MDACC Adverse Event Reporting Policy for Leukemia Phase I and early Phase II studies.

The descriptions and grading scales found in the revised NCI Common Terminology Criteria for Adverse Events (CTCAE) version 3.0 will be utilized for adverse event reporting. (http://ctep.cancer.gov/reporting/ctc.html).

Serious Adverse Event Reporting (SAE)

A serious adverse event is – any adverse drug experience occurring at any dose that results in any of the following outcomes:

- Death
- A life-threatening adverse drug experience any adverse experience that places the patient, in the view of the initial reporter, at immediate risk of death from the adverse experience as it occurred. It does not include an adverse experience that, had it occurred in a more severe form, might have caused death.
- Inpatient hospitalization or prolongation of existing hospitalization
- A persistent or significant disability/incapacity a substantial disruption of a person's ability to conduct normal life functions.
- A congenital anomaly/birth defect.

Important medical events that may not result in death, be life-threatening, or require hospitalization may be considered a serious adverse drug experience when, based upon appropriate medical judgment, they may jeopardize the patient or subject and may require medical or surgical intervention to prevent one of the outcomes listed in this definition. Examples of such medical events include allergic bronchospasm requiring intensive treatment in an emergency room or at home, blood dyscrasias or convulsions that do not result in inpatient hospitalization, or the development of drug dependency or drug abuse (21 CFR 312.32).

- Important medical events as defined above, may also be considered serious adverse events. Any important medical event can and should be reported as an SAE if deemed appropriate by the Principal Investigator or Sponsor.
- All events occurring during the conduct of a protocol and meeting the definition of a SAE must by reported to the IRB in accordance with the timeframes and procedures outlined in "University of Texas M. D. Anderson Cancer Center Institutional Review Board Policy". SAEs must be reported to the IRB and the Sponsor (Safety Project Manager) regardless of attribution.
- All life-threatening or fatal events with possible, probable or definite attribution

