 to the study drug must have a written report faxed within 24 hours (next working
 day) of knowledge of the event to the Safety Project Manager in the Office of
 Research Education and Regulatory Management (ORE&RM) ([contact]). The sponsor representative should be notified by phone at [contact]
 to confirm receipt of the fax.
- The MDACC Internal Adverse Event Reporting Form will be used for reporting to the IRB and the Sponsor (Safety Project Manager ORE&RM).
- Serious adverse events will be captured from the time the patient signs
 consent until 30 days after the last dose of drug. Serious adverse events
 must be followed until clinical recovery is complete and laboratory test
 have returned to baseline, progression of the event has stabilized, or there
 has been acceptable resolution of the event.
- Additionally, any serious adverse events that occur after the 30 day time period that are related to the study treatment must be reported to the IRB and the Sponsor (Safety Project Manager ORE&RM). This may include the development of a secondary malignancy.

Reporting to FDA:

 Serious adverse events will be forwarded to FDA by the Sponsor (Safety Project Manager ORE&RM) according to 21 CFR 312.32.

It is the responsibility of the PI and the research team to ensure serious adverse events are reported according to the Code of Federal Regulations, Good Clinical Practices, the protocol guidelines, the sponsor's guidelines, and Institutional Review Board policy.

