9.5 Reporting and Exclusions

9.5.1 Evaluation of toxicity.

All patients will be evaluable for toxicity from the time of their first treatment with INCB018424.

9.5.2 Evaluation of response.

All patients included in the study must be assessed for response to treatment, unless there are major protocol treatment deviations or they are ineligible. Each patient will be assigned one of the following categories: 1) complete response, 2) partial response, 3) stable disease, 4) progressive disease, 5) early death from malignant disease, 6) early death from toxicity, 7) early death because of other

cause, or 8) unknown (not assessable, insufficient data). [Note: By arbitrary convention, category 9 usually designates the "unknown" status of any type of data in a clinical database.]

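### Read literally, the only rule that stops a cohort for toxicity does not count a rapid drug-related death

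*Combined protocol and SAP*

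**What the plan says.** Section 9.1.1, repeating section 4.1, splits patients into cohort I (AML, ALL, MDS including CMML, blast phase CML) and cohort II (chronic phase CML). Once 6 patients are enrolled, cohort I stops when at least 30% of its patients have "grade 3 or 4 toxicity thought to be directly related to INCB018424 and lasting longer than 2 weeks". Cohort II has the same rule with a 15% limit. No other text stops a cohort for toxicity.

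Three other provisions bear on a toxic death:

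- Section 4.2, lead-in: in each arm "three patients will be initially treated and observed for toxicity for one treatment cycle (28 days) before the additional seven patients are entered". No limit is attached.
- Section 4.2, dose-reduction list: "Dose reduction will be considered if the number of patients experiencing grade 3 or higher toxicities exceed" a list beginning 2/3, 3/4, 4/7, 5/10.
- Section 8: "SAEs must be reported to the IRB and the Sponsor (Safety Project Manager) regardless of attribution". A faxed report within 24 hours, glossed as the next working day, applies where the drug is implicated: "All life-threatening or fatal events with possible, probable or definite attribution".

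Section 9.5.2 includes among its response categories "6) early death from toxicity", so the plan foresees fatal toxicity.

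**The concern.** To count towards stopping, a toxicity must be grade 3 or 4, directly related to the drug, and last more than 2 weeks. The duration condition makes sense for reversible toxicity, where persistence measures severity. It has no such meaning for a death. By itself it excludes a drug-related death soon after onset, however the grading scale numbers a fatal event.

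The stated limit therefore ranks a 15-day grade 3 event above a rapid drug death. Stopping for rapid deaths would rest on case-by-case judgement after SAE reports, which a numerical limit is meant to supplement.

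Serious toxicity is not remote. Section 2.2.3 reports that dosing at 50 mg BID in myelofibrosis was halted after two of four patients had significant falls in neutrophils and platelets. Section 4.1 allows patients with progressive disease, other than those with chronic phase CML, to escalate to that dose.

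**Working it through.** **1. The provisions side by side**

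| Provision | Would it register a rapid drug death? | Does it set a limit that stops a cohort? |
|---|---|---|
| 4.1 / 9.1.1 stopping rule | No, unless more than 2 weeks of grade 3-4 toxicity came first | Yes: 30% or 15% |
| 4.2 three-patient hold | Yes, by observation | No limit given |
| 4.2 dose-reduction list | Yes: grade 3 or higher, no duration condition | No. Dose reduction is considered. Counts must exceed 2/3, so it is first crossed at 3/3 |
| Section 8 SAE reporting | Yes | No limit given |
| 4.4 unacceptable adverse event | Ends treatment for that patient | No |

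**2. Counts that need no assumed rates**

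The smallest counts that stop (count/n at or above the limit) are 2/6, 3/10, 6/20 and 9/30 in cohort I, and 1/6, 2/10, 3/20 and 5/30 in cohort II. With the first check at patient 6:

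- Cohort I, two 15-day grade 3 events: 2/6 = 33%, stop. Two rapid drug deaths: 0/6, continue.
- Cohort II, one rapid drug death: 0/6, continue, although 1/6 = 17% would exceed 15%.
- Six rapid drug deaths in six patients: 0/6, continue in either cohort.

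If the rule is instead first checked at patient 7, the same contrast needs 3/7 = 43% in cohort I and 2/7 = 29% in cohort II.

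**3. Chance of stopping**

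The plan gives no operating characteristics for this rule, so there is no figure of its own to reproduce. Assumptions, none from the documents:

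- q = 0.10 is the rate of qualifying grade 3-4 toxicity.
- d is the rate of rapid drug-related death without it, taken as 0.01, 0.02 and 0.05.
- Each outcome is known before the next patient enters.

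The horizon is N = 30. For cohort I that is the first stage of AML, ALL and MDS at 10 each. For cohort II it is the CML maximum if all are chronic phase.

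Let f_n(k) be the probability of reaching n patients, not yet stopped, with k counted. Then

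f_n(k) = (1 − p) f_{n−1}(k) + p f_{n−1}(k − 1),

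and at each check any probability with k/n at or above the limit moves to the stopped state. As written, p = q. With deaths counted, p = q + d.

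The first check, at n = 6, can be done by hand:

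- Cohort I (k ≥ 2), as written: 1 − 0.90^6 − 6(0.10)(0.90^5) = 1 − 0.531 − 0.354 = 0.114 (from unrounded terms). With d = 0.02: 1 − 0.88^6 − 6(0.12)(0.88^5) = 1 − 0.464 − 0.380 = 0.156.
- Cohort II (k ≥ 1), as written: 1 − 0.90^6 = 0.469. With d = 0.02: 1 − 0.88^6 = 0.536.

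Running the recursion to N = 30:

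| Cohort, first check | As written | d = 0.01 | d = 0.02 | d = 0.05 |
|---|---|---|---|---|
| I, patient 6 | 0.142 | 0.170 | 0.200 | 0.301 |
| I, patient 7 | 0.080 | 0.103 | 0.128 | 0.220 |
| II, patient 6 | 0.603 | 0.653 | 0.698 | 0.811 |
| II, patient 7 | 0.469 | 0.530 | 0.588 | 0.736 |

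The as-written column does not change with d, because the rule does not see these deaths. For cohort II at N = 10, the first stage of CML, with the first check at patient 6, the figures are 0.496 as written and 0.570 with d = 0.02.

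**The case against.** The strongest reply is that no sensible team would score a drug death below a 15-day grade 3 event. On this view the text is a drafting slip, and deaths already reach people who can act: each arm pauses after three patients, the 4.2 list takes in fatal events, and attributed deaths are reported within a working day. This stands to the extent that such deaths would be noticed. It does not supply a limit. If deaths were meant to count, saying so costs nothing; if they were not, the rule is deficient. Section 4.2 shows that wider wording was available.

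The reporting safeguard also has gaps. Section 8.1 sends myelosuppression and complications such as infection and bleeding to the study summary, although its table of exclusions for blood and infection events covers only grades 1-4.

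The rates are illustrative, and at d = 2% the cohort I contrast is rare: two or more rapid deaths in six patients has probability 1 − 0.98^6 − 6(0.02)(0.98^5) = 0.6%. That is fair. In cohort II one death is enough, with probability 1 − 0.98^6 = 11%. The recursion is also idealised, because outcomes that need more than 2 weeks to establish will not be known before each new entry, and the three-patient holds are not modelled. The case rests on the wording and the counts rather than on these percentages.

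Finally, the remedy is limited. A single rapid death in the first six cohort I patients (1/6 = 17%) would still not stop the cohort, and the 15% limit in cohort II is already sensitive. Both points stand.

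**Conclusion.** The concern holds and should be fixed. On its literal terms, the only limit that stops a cohort omits the most severe outcome unless more than 2 weeks of grade 3-4 toxicity came before it. This conclusion rests on the text alone. At the assumed 10% plus 2%, counting deaths changes the chance of stopping by 30 patients by about 6 percentage points in cohort I and about 10 in cohort II (about 5 and 12 if first checked at patient 7). Those sizes depend on rates that the documents do not give. The response design is untouched.

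**What to change.** In sections 4.1 and 9.1.1, keep the present event and add an alternative: *or any fatal (grade 5) toxicity thought to be directly related to INCB018424, regardless of duration*, with each patient counted once. Leave the 30% and 15% limits as they are. While editing, state whether the first check is at patient 6 or patient 7.

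The cost is one clause in two places, with no additional data. The price is more frequent stopping, larger in cohort II. Single deaths in cohort I will still depend on judgement after SAE reports, and the protocol should say so.
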